4.4 Permissible and Prohibited Medications/Treatments

4.4.1 Permissible Medications/Treatments

All medications and treatments are permitted with the exception of the restricted medications and treatments described in Section 4.4.2.

The use of any concomitant medication, prescription or over-the-counter, is to be recorded on the subject's electronic case report form (eCRF) at each visit along with the reason the medication is taken.

Therapy considered necessary for the subject's welfare may be given at the discretion of the investigator. If the permissibility of a specific medication/treatment is in question, please contact Allergan.

4.4.2 Prohibited Medications/Treatments

Concurrent enrollment in another clinical investigation for a medicinal product or device is prohibited. Subjects must not be on an ongoing regimen of anti-coagulant medications (eg, warfarin). Subjects must not be on an ongoing regimen of medications or other substances known to increase coagulation time (eg, aspirin; ibuprofen; high doses of Vitamin C or Vitamin E; herbal supplements with garlic, ginkgo biloba, or ginseng) within 10 days prior to and 3 days after study device injection.

Subjects must not use lip plumping product or begin any new regimen of over-the-counter or prescription, oral or topical, antiwrinkle products for the lips or around the mouth. Subjects must not undergo facial tissue augmentation with dermal fillers or fat injections, semi-permanent fillers or permanent facial implants, botulinum toxin injections, mesotherapy, or cosmetic facial procedures (eg, face-lift, laser, photomodulation, intense pulsed light, radio frequency, dermabrasion, moderate or greater depth chemical peel, or other ablative procedures) below the inferior orbital rim at any time during the study.

The decision to administer a prohibited medication/treatment is done with the safety of the study participant as the primary consideration. When possible, Allergan is to be notified before the prohibited medication/treatment is administered.

4.4.3 Escape Medications

Administration of hyaluronidase should not be performed during the study.

4.4.4 Special Diet or Activities

Within the first 24 hours after treatment, subjects should avoid strenuous exercise, extensive sun or heat exposure, and alcoholic beverages. Exposure to any of the above may cause temporary redness, swelling, and/or itching at the injection site.

4.5 Treatment Allocation Ratio and Stratification

Subjects will be randomized at a 3:1 ratio either to have treatment with VOLBELLA with Lidocaine at the outset of the study (treatment group) or to have treatment delayed by 3 months (no-treatment control group). Randomization will be stratified by baseline LFS score (ie, LFS score rated as Minimal, Mild, or Moderate at the randomization visit by the Evaluating Investigator).

5. Study Population

5.1 Number of Subjects

An estimated 176 subjects will be randomized in a 3:1 ratio resulting in 132 subjects assigned to the VOLBELLA with Lidocaine group and 44 subjects assigned to the no-treatment control group. Approximately 148 subjects including 111 treated subjects and 37 untreated control subjects will complete the 3-month visit (primary endpoint) with an anticipated dropout rate of 15% by month 3. An estimated 133 subjects will complete the 12-month visit (end of study) based on an anticipated dropout rate of 10% after month 3.

5.2 Study Population Characteristics

Subjects will be recruited from a population of healthy Chinese adults who desire lip enhancement.

5.3 Inclusion Criteria

The following are requirements for entry into the study:

1. male or female, 18 years of age or older
2. has an overall baseline score of Minimal, Mild, or Moderate on the 5-point LFS, as assessed by the Evaluating Investigator, and desires to achieve at least a 1-point improvement in overall LFS score after treatment

[REDACTED]

4. has the ability to follow study instructions and is likely to complete all required visits

[REDACTED]

5.4 Exclusion Criteria

The following are criteria for exclusion from participating in the study:

[REDACTED]

[REDACTED]

[Redacted text block containing multiple paragraphs of obscured information]

10. is on an ongoing regimen of anti-coagulation therapy (eg, warfarin)

Approval Date: 29-Jul-2015

[Redacted text block]

[Redacted text block]

[Redacted text block]

- 14. has current cutaneous inflammatory or infectious processes (eg, acne or herpes), an abscess, an unhealed wound, or a cancerous or precancerous lesion in the mouth area (study treatment may be delayed so that subjects with a history of recurrent oral herpes can take prophylactic antiviral/herpes medication for 2 days)

[Redacted text block]

[Redacted text block]

[Redacted text block]

[Redacted text block]

[Redacted text block]

Approval Date: 29-Jul-2015

[REDACTED]

6. Procedures

6.1 Washout or Run-In Intervals

6.1.1 Washout Intervals

Washout Period	Medication or Procedure
10 days before treatment	
• medications known to increase coagulation time (eg, aspirin or ibuprofen)• other pharmaceutical, vitamin, or herbal preparations with clinically significant anticoagulation effects (eg, high doses of Vitamin C or Vitamin E, herbal supplements with garlic, ginkgo biloba, or ginseng) 
NOTE: This 10-day washout period for anticoagulants must continue for 3 days after treatment is administered.

10 days before enrollment	
• lip plumping products
30 days before enrollment	
• any investigational product

6.1.2 Run-in Intervals

Run-In Period	Medication or Procedure
2 days before treatment	
• prophylactic herpes treatment for subjects with a history of recurrent oral herpes lesions
30 days before enrollment	
• over-the-counter or prescription, oral or topical, anti-wrinkle products for the lips or around the mouth for subjects who will use such products during the study

[REDACTED]

Approval Date: 29-Jul-2015

[Redacted text block]

[Redacted text block]

[Redacted text block]

[Redacted text block]

[Redacted text block]

[Redacted text block]

[Redacted text block]

[Redacted text block]

Approval Date: 29-Jul-2015

[Redacted]

[Redacted]

[Redacted]

[Redacted]

[Redacted]

[Redacted]

[Redacted]

[Redacted]

[Redacted]

Approval Date: 29-Jul-2015

[REDACTED]

[REDACTED]

- [REDACTED]
- [REDACTED]
- [REDACTED]
- [REDACTED]
- [REDACTED]

[REDACTED]

[REDACTED]

Approval Date: 29-Jul-2015

[Redacted text block containing multiple paragraphs and bulleted points]

Approval Date: 29-Jul-2015

[Redacted text block]

[Redacted text block]

[Redacted text block]

[Redacted text block]

[Redacted text block]

[Redacted text block]

[Redacted text block]

[Redacted text block]

[Redacted text block]

[Redacted text block]

Approval Date: 29-Jul-2015

[Redacted text block]

[Redacted text block]

[Redacted text block]

[Redacted text block]

[Redacted text block]

[Redacted text block]

[Redacted text block]

[Redacted text block]

[Redacted text block]

Approval Date: 29-Jul-2015

6.3 Instructions for the Subjects

At the screening visit, the Treating Investigator (or designee) will discuss routine alternative treatments that may be available with any subject who is interested in participating in the study. The available alternative treatments include plastic surgery, autologous fat injection, etc; he/she will counsel the subject regarding his/her treatment goals, and the potential benefit and limitations of study treatment. After counseling, if the subject's expectations are not realistic, the Treating Investigator (or designee) will not proceed with obtaining the subject's signature on the ICF and will discontinue the subject from the study.

During each study visit, subjects will be required to remove all jewelry, make-up, and lipstick, and male subjects will not be allowed to have facial hair in the perioral area to avoid interference with the digital photographs.

For 10 days before and 3 days after study treatment administration, subjects should avoid taking anti-coagulation, antiplatelet, or thrombolytic medications; nonsteroidal anti-inflammatory drugs; supplements of Vitamin C or E, garlic, ginkgo biloba, or ginseng; or other supplements known to increase coagulation time. These precautions are recommended to reduce the risk of posttreatment bleeding or bruising.

For at least 24 hours after treatment, subjects should avoid strenuous exercise, consumption of alcoholic beverages, and extended exposure to sun or heat to reduce the risk of posttreatment redness, swelling, and/or itching.

Subjects will also be instructed to contact the Treating Investigator or his/her research staff to report any unexpected symptoms or to ask questions about the study.

6.4 Unscheduled Visits

An unscheduled visit may occur for safety purposes (eg, if the subject needs to obtain information regarding adverse events or ISRs). An unscheduled visit may also occur to repeat facial digital images if those obtained at the scheduled visit are poor quality images. Applicable procedures will be performed and recorded on the eCRF.

Approval Date: 29-Jul-2015

6.5 Early Discontinuation of Subjects

Each subject reserves the right to withdraw from the study at any time without jeopardy to his/her future medical care. All follow-up procedures scheduled to be performed at the final site visit should be performed at the subject's last site visit. Subjects may also be administratively withdrawn if they do not return for follow-up visits. For any subject who withdraws from the study, the date and reason for withdrawal will be recorded on the eCRF. If an adverse event is ongoing at the time of withdrawal, the Treating Investigator will attempt to follow the subject until the adverse event has been resolved or follow-up is no longer possible. The Treating Investigator shall ask for the subject's permission to follow his/her status/condition outside the study.

Randomized subjects who withdraw before treatment will not be replaced by another subject. The subject number and associated randomization number of the withdrawn subject should not be reassigned to a different subject.

If a subject fails to return for 1 or more scheduled study visits, the Treating Investigator (or designee) will attempt to contact the subject to determine and document the reason the subject has failed to return and to encourage compliance with the study visit schedule.

At regular intervals, the Treating Investigator (or designee) will record on the eCRF and will report to Allergan and the Independent Ethics Committee (IEC) the reasons for which any subjects are discontinued from the study, including subjects who signed the ICF but do not proceed to randomization.

6.6 Withdrawal Criteria

The subject may withdraw at will at any time for any reason.

7. Response Measures and Summary of Data Collection Methods

7.1 Effectiveness Measures

7.1.1 Primary Effectiveness Measure

The primary effectiveness measure is the Evaluating Investigator's assessment of overall lip fullness using the LFS described in Table 4.

Table 4 5-Point Lip Fullness Scale

Score	Grade	Description
4	Very Marked	Very significant red lip show, lower lip pout, and upper lip pout
3	Marked	Significant red lip show and lower lip pout
2	Moderate	Moderate red lip show with slight lower lip pout
1	Mild	Some red lip show; no lower lip pout
0	Minimal	Flat or nearly flat contour, minimal red lip show

7.1.2 Secondary Effectiveness Measures

The secondary effectiveness measures are the subject’s assessment of overall lip fullness using the 5-point LFS, the volume of the overall lips measured from 3D images, and the lip surface area measured from 3D images.

[REDACTED]

[REDACTED]	[REDACTED]	[REDACTED]
[REDACTED]	[REDACTED]	[REDACTED]
[REDACTED]	[REDACTED]	[REDACTED]
[REDACTED]	[REDACTED]	[REDACTED]
[REDACTED]	[REDACTED]	[REDACTED]

7.2 Safety Measures

Safety measures will include:

- subject assessment of procedural pain (pain during injection) on an 11-point scale ranging from 0 (no pain) to 10 (worst pain imaginable)
- severity and duration of ISRs, which will be obtained by a subject safety diary

Approval Date: 29-Jul-2015

- adverse events reported to and recorded by the investigators

Vital sign measurements, including blood pressure (systolic and diastolic, while subject is seated), temperature, pulse, and respiratory rate, will be performed at screening, treatment visit, Month 1, Month 3 and Month 6 visits. Urine pregnancy tests for women of childbearing potential (sexually active and not sterile, surgically sterilized, or postmenopausal for at least 1 year) will be performed at screening, treatment visit, and the month 6 posttreatment follow-up visit. Routine hematology and blood chemistry testing and urinalysis will be performed at screening and at the months 1 and 6 posttreatment follow-up visit.

7.3 Demographics and Baseline Characteristics

Subject demographics and baseline characteristics to be collected include sex, age, height, weight, Fitzpatrick skin phototype and sun exposure, smoking history, medical/surgical/cosmetic/dental procedure history, and prior medications.

7.4 Treatment Characteristics

Treatment characteristics will be evaluated by collecting information on anesthesia usage, treatment area, injection ease, and volume injected.

7.5 Summary of Methods of Data Collection

Electronic data capture will be used to collect study-specific information, such as subject and investigator assessments. Completed eCRFs will be reviewed by the Treating or Evaluating Investigator as applicable (or designee), and the designated monitor will verify the data. Investigators will provide access to hospital files, medical records, and other source documents containing subject clinical/medical information. Source document verification will be performed.

Subjects will either complete the ISR diaries electronically, or they will complete them on paper, and responses will be entered into the clinical database. Sites will save photographs onto supplied electronic media and send the storage device to [REDACTED]. Alternatively, files containing the facial digital photographs may be directly uploaded to [REDACTED].

8. Statistical Procedures

One database lock is planned after all subjects exit the study. A statistical analysis plan will be prepared to provide specifications for all analyses. The plan will be finalized and approved prior to clinical database lock.

8.1 Analysis Populations

The following analysis populations will be used in the analyses for this study:

- modified intent-to-treat (mITT) population: subjects who are randomized to study treatment (treatment group) and receive at least 1 study device treatment and have baseline and at least 1 posttreatment assessment of the primary variable, and subjects who are randomized to the no-treatment control group and have baseline and at least 1 follow-up assessment of the primary variable
- per-protocol (PP) population: all mITT subjects who do not have any significant protocol deviations affecting the primary effectiveness endpoint
- safety population: subjects who receive at least 1 study treatment

Unless specified otherwise, effectiveness analyses will be conducted using the mITT population. The PP population will be used to perform sensitivity analyses for the primary effectiveness variable. All safety analyses will be conducted using the safety population.

8.2 Collection/Derivation of Primary and Secondary Effectiveness Assessments

8.2.1 Primary Effectiveness Variable

The primary effectiveness variable is lip response based on the Evaluating Investigator's assessment of overall lip fullness using the 5-point LFS. A subject showing ≥ 1 -point improvement (increase in fullness) in LFS score compared with baseline will be considered to be a lip responder. The primary evaluation timepoint is month 3 after last treatment for subjects in the VOLBELLA with Lidocaine group and month 3 after randomization for subjects in the no-treatment control group.

8.2.2 Secondary Effectiveness Variables

The 3 secondary effectiveness variables are:

- subject's lip response based on the subject's assessments of overall lip fullness using the 5-point LFS
 - A subject showing ≥ 1 -point improvement (increase in fullness) in 5-point LFS score compared with baseline will be considered to be a lip responder. The evaluation timepoint is month 3 after last treatment for subjects in the VOLBELLA with Lidocaine group.
- percentage change from baseline to month 3 in overall lip volume
 - The evaluation timepoint is month 3 after last treatment for subjects in the VOLBELLA with Lidocaine group and month 3 after randomization for subjects in the no-treatment control group.
- change from baseline to month 3 in lip surface area
 - The percentage change from baseline in lip surface area will be calculated as the difference (ie, month 3 lip surface area minus the baseline lip surface area) divided by baseline value. Month 3 refers to 3 months after last treatment for subjects in the VOLBELLA with Lidocaine group and 3 months after randomization for subjects in the no-treatment control group.

8.3 Hypothesis and Methods of Analysis

In general, descriptive statistics will be presented. Categorical variables will be summarized with frequency and percentage. Continuous variables will be summarized by number of subjects, mean, median, standard deviation, minimum, and maximum. Where appropriate, 2-sided 95% confidence intervals (CIs) for mean or proportion will be provided as part of the descriptive summary.

Unless otherwise noted, during posttreatment follow-up visits (for both the VOLBELLA with Lidocaine group and the no-treatment control group), baseline refers to the last evaluation prior to initial treatment; during the no-treatment period (for the no-treatment control group), baseline refers to the last evaluation prior to the month 1 visit.

No imputation for missing data will be performed. However, sensitivity analyses for the primary endpoint will be performed using applicable missing imputations to assess the potential effect of missing data.

8.3.1 Primary Effectiveness Analyses

The primary effectiveness analysis will test for superiority of VOLBELLA with Lidocaine over no treatment in the difference in overall lip fullness responder rate based on the Evaluating Investigator's assessment at month 3. Month 3 refers to 3 months after the last treatment for subjects in the VOLBELLA with Lidocaine group and 3 months after randomization for subjects in the no-treatment control group.

The null hypothesis is that the responder rate for VOLBELLA with Lidocaine group is equal to the responder rate for the no-treatment control group. The alternative hypothesis is that the responder rates are not equal for the VOLBELLA with Lidocaine and the no-treatment control groups. These hypotheses are stated as:

$$H_0: P_v - P_c = 0$$

$$H_a: P_v - P_c > 0 \text{ or } P_v - P_c < 0$$

where P_v and P_c denote the responder rates for the VOLBELLA with Lidocaine group at month 3 after last treatment and no-treatment control group at month 3 after randomization, respectively. Two-sided Fisher's exact test with 5% significance level will be used to compare treatment effects between VOLBELLA with Lidocaine and the no-treatment control group. If the 2-sided p-value is less than 0.05 and the responder rate is greater for VOLBELLA with Lidocaine than for the no-treatment control group, then VOLBELLA with Lidocaine will be considered superior to the no-treatment control group. The primary effectiveness analysis will be performed on the mITT population.

8.3.2 Secondary Effectiveness Analyses

The following analyses will be performed for each of the secondary effectiveness endpoints:

- For overall lip fullness based on the subject's assessments using the 5-point LFS, responder rate and 95% exact CI will be presented only for the treatment group at month 3.

- The overall lip volume change from baseline to month 3 will be summarized using descriptive statistics. Treatment effect will be analyzed using t-test or Wilcoxon rank-sum test as appropriate.
- The lip surface area percentage change from baseline to month 3 will be summarized descriptively. Treatment effect for this endpoint will be analyzed using t-test or Wilcoxon rank-sum test, as appropriate.

[REDACTED]

[REDACTED]

[REDACTED]

[REDACTED]

[REDACTED]

[REDACTED]

[REDACTED]

[REDACTED]

[REDACTED]

[REDACTED]

[REDACTED]

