The primary effectiveness analysis will test for superiority of VOLBELLA with Lidocaine over no treatment in the difference in overall lip fullness responder rate. Two-sided Fisher's exact test with 5% significance level will be used to compare treatment effects between VOLBELLA with Lidocaine group and the no-treatment control group. If the 2-sided p-value is less than 0.05 and the responder rate is greater for the VOLBELLA with Lidocaine group than for the no-treatment control group, then VOLBELLA with Lidocaine will be considered superior to no-treatment.

Secondary effectiveness analyses will include 1) responder rate and the corresponding 2-sided 95% exact CI based on the subject's assessment of overall lip fullness at month 3 for the treatment group, 2) change from baseline to month 3 in volume of the overall lips, and 3) the percentage change from baseline to month 3 in lip surface area using t-test or Wilcoxon rank-sum test, as appropriate.

All effectiveness analyses will be performed on the modified intent-to-treat (mITT) population, defined as all subjects who are randomized to study treatment (treatment group), receive at least 1 study device treatment, and have baseline and at least 1 posttreatment assessment of the primary variable, and subjects who are randomized to the no-treatment control group and have baseline and at least 1 follow-up assessment of the primary variable. Additional sensitivity analyses for the primary effectiveness variable will be performed on the per-protocol (PP) population, defined as all mITT subjects who do not have any significant protocol deviations that affect the primary effectiveness endpoint. All analyses will be performed without data imputation.

Safety: Procedural pain will be summarized using descriptive statistics. ISRs reported in subject diaries will be summarized by treatment (initial and touch-up), symptom, maximum reported severity, and maximum reported duration. Summaries will include the incidence rate for each ISR.

Adverse events will be summarized by System Organ Class and Preferred Term and will be tabulated by duration, severity, causality, action taken, relationship to treatment, and outcome. The summary will include incidence rate as well as total number of events.

Table of Contents

Synopsis	3
Table of Contents	7
List of Tables.....	10
1. Abbreviations and Terms	17
2. Background, Risk and Benefit, and Clinical Rationale	18
2.1 Background	18
2.2 Risk and Benefit.....	20

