**Table 4-1 Study Objectives and Corresponding Endpoints**

[figure not shown]
Objectives	Endpoints

 
To evaluate and compare the effectiveness of Volbella with no-treatment control in lip enhancement among Chinese population
 
	
Primary Endpoint
 
 
Responder at Month 3 (Subject showing <math>\geq</math> 1-point improvement (increase in fullness)) in LFS score compared with baseline as assessed by EI
 
 
Secondary Endpoint(s)
 
 
Responder at Month 3 (Subject showing <math>\geq</math> 1-point improvement (increase in fullness)) in LFS score compared with baseline as assessed by subject
 
Change from baseline to month 3 in overall lip volume as measured from 3D images
 
Percentage change from baseline to month 3 in lip surface area as measured from 3D images
 

 
To evaluate the safety of Volbella in lip enhancement among Chinese population
 
	
Safety Assessments
 
 
Study treatment exposure
 
Adverse events (AE)
 
Injection site responses (ISR)
 
Procedural pain
 
Clinical laboratory values (routine hematology and blood chemistry testing and urinalysis)
 

[figure not shown]
---

[figure not shown]
	

• Vital sign

• Physical measurement

• EKG

• Urine pregnancy test

--	--

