CFB Wilcoxon test	
 
• Continuous descriptives for baseline, postbaseline, and CFB values
 
• For comparing VOLBELLA group vs. no-treatment control group during UCP (Volbella minus control)               
 
◦ Mean differences
 
◦ P-values and 95% CI from Wilcoxon rank-sum test
 
 
 
• N included = subjects with non-missing values at both baseline and the specified postbaseline analysis visit
 

Responder exact test	
 
• Categorical descriptives for responders
 
• Exact binomial 95% CI of percentages within group
 
• For comparing VOLBELLA group vs. no-treatment control group during UCP (VOLBELLA minus control)               
 
◦ Responder rate difference
 
◦ 95% exact unconditional confidence interval
 
◦ P-value from 2-sided Fisher's exact test
 
 
 
• N included = with non-missing values at both baseline and the specified postbaseline analysis visit
 

Responder exact 95% CI within group (treatment group only)	
 
• Categorical descriptives for responders
 
• Exact binomial 95% CI of percentages within group
 
• N included = with non-missing values at both baseline and the specified postbaseline analysis visit
 

Responder CMH	
 
• Categorical descriptives for responders
 

Methodology	Description
test	
 
• Responder rate differences for VOLBELLA group vs. no-treatment group during UCP
 
• P-values from Cochran-Mantel-Haenszel test stratified by baseline characteristic comparing VOLBELLA group vs. no-treatment group during UCP
 
• N included = with non-missing values at both baseline and the specified postbaseline analysis visit
 

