**Table 5-16 Secondary Effectiveness Analyses**

Endpoint	Description	Timing	Methodology
LFS responder as assessed by subject	Number (%) of responders by treatment group	Month 3	Responder exact test within group (treatment group only)
Change from baseline in overall lip volume	Summary by treatment group	Month 3	CFB 2-sample t-test or Wilcoxon test
Percentage change from baseline in lip surface area	Summary by treatment group	Month 3	CFB 2-sample t-test or Wilcoxon test

[REDACTED]

[REDACTED]

[REDACTED]

[REDACTED]

[REDACTED]

[REDACTED]

[REDACTED]

[REDACTED]

[REDACTED]

[REDACTED]

[REDACTED]

[REDACTED]

[REDACTED]

[REDACTED]

[REDACTED]

[REDACTED]

[REDACTED]

[REDACTED]

[REDACTED]

[REDACTED]	[REDACTED]	[REDACTED]	[REDACTED]
[REDACTED]	[REDACTED]	[REDACTED]	[REDACTED]
[REDACTED]	[REDACTED]	[REDACTED]	[REDACTED]
[REDACTED]	[REDACTED]	[REDACTED]	[REDACTED]
[REDACTED]	[REDACTED]	[REDACTED]	[REDACTED]
[REDACTED]	[REDACTED]	[REDACTED]	[REDACTED]
[REDACTED]	[REDACTED]	[REDACTED]	[REDACTED]
[REDACTED]	[REDACTED]	[REDACTED]	[REDACTED]
[REDACTED]	[REDACTED]	[REDACTED]	[REDACTED]
[REDACTED]	[REDACTED]	[REDACTED]	[REDACTED]
[REDACTED]	[REDACTED]	[REDACTED]	[REDACTED]
[REDACTED]	[REDACTED]	[REDACTED]	[REDACTED]
[REDACTED]	[REDACTED]	[REDACTED]	[REDACTED]
[REDACTED]	[REDACTED]	[REDACTED]	[REDACTED]
[REDACTED]	[REDACTED]	[REDACTED]	[REDACTED]
[REDACTED]	[REDACTED]	[REDACTED]	[REDACTED]
[REDACTED]	[REDACTED]	[REDACTED]	[REDACTED]
[REDACTED]	[REDACTED]	[REDACTED]	[REDACTED]
[REDACTED]	[REDACTED]	[REDACTED]	[REDACTED]
[REDACTED]	[REDACTED]	[REDACTED]	[REDACTED]
[REDACTED]	[REDACTED]	[REDACTED]	[REDACTED]
[REDACTED]	[REDACTED]	[REDACTED]	[REDACTED]

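### The two between-arm secondary endpoints ignore baseline value and LFS stratum, and the SAP's Wilcoxon row pairs a mean difference with a rank-based interval

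*Protocol*

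**What the plan says.** Three secondary effectiveness endpoints are planned. The subject-rated LFS response is reported for the treatment group only, so two endpoints are compared between arms: lip volume and lip surface area, both at month 3.

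- **Method.** For lip volume, Protocol 8.3.2 states "Treatment effect will be analyzed using t-test or Wilcoxon rank-sum test as appropriate", with a matching sentence for surface area. SAP Table 5-16 gives both endpoints the entry "CFB 2-sample t-test or Wilcoxon test". No rule for choosing between the tests appears in the readable text.
- **Stratification.** Protocol 4.5 states "Randomization will be stratified by baseline LFS score". The only stratified method in SAP Table 5-2 is a Cochran-Mantel-Haenszel test for responders, and Tables 5-15 and 5-16 do not assign it.
- **Reported quantities.** In SAP Table 5-2 the t-test row gives the mean difference with the t-test's p-value and interval. The Wilcoxon row keeps the mean difference but replaces the rest with "P-values and 95% CI from Wilcoxon rank-sum test".
- **Endpoint labels.** Protocol 8.2.2 lists "percentage change from baseline to month 3 in overall lip volume" and "change from baseline to month 3 in lip surface area". Its own sub-item then defines surface area as a percentage. Elsewhere volume is an absolute change: the synopsis has "change from baseline to month 3 in volume of the overall lips" and SAP Table 4-1 has "Change from baseline to month 3 in overall lip volume as measured from 3D images". Protocol 8.3.2 and SAP Table 5-16 agree with these.

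**The concern.** There are two main issues.

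1. **Unused information.** Baseline enters only through the change or percentage change. A change score fixes the baseline slope at 1, which is generally not the most precise choice. The stratum is also left out. With only about 37 controls expected at month 3, precision in that arm is limited.

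2. **Estimate and interval describe different quantities.** Inverting a rank-sum test gives an interval for a location shift (the Hodges-Lehmann interval), not for a difference in means. The SAP does not use that term, but that is what such an interval estimates. The two quantities agree when the arms have the same shape. They separate when one arm is skewed, which is the usual reason to choose Wilcoxon. A differing shape is plausible here, because injected lips may respond variably while untreated lips should change little.

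At stake is how these two effects are reported. No success criterion is attached to them, and the primary superiority test does not depend on them.

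**Working it through.** **Inputs.** From Protocol 4.5 and 8.5: 3:1 allocation, with 111 treated and 37 control subjects expected at month 3. The documents give no SD, effect size or baseline correlation for volume or area, so those below are assumed. The only power figure is for the primary endpoint. It reproduces: exact enumeration of the two-sided Fisher test at 79.0% versus 44.1% gives 96.7%, against a stated figure above 96%. Nothing below changes it.

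**1. Baseline adjustment, equal variances.** Let σ² be the variance at each time point and ρ the correlation between baseline and month 3.

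- Variance of the change score: 2σ²(1−ρ)
- Residual variance under ANCOVA: σ²(1−ρ²)
- Ratio: (1−ρ²) / [2(1−ρ)] = (1+ρ)/2

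| ρ (assumed) | Variance ratio | CI width ratio | CI narrower by | ANCOVA power where the unadjusted test has 80% (d = 0.53 SD of change) |
|---|---|---|---|---|
| 0.5 | 0.75 | 0.866 | 13% | 89.9% |
| 0.7 | 0.85 | 0.922 | 8% | 86.0% |
| 0.8 | 0.90 | 0.949 | 5% | 84.0% |
| 0.9 | 0.95 | 0.975 | 3% | 82.0% |

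The formula holds for absolute change and is only approximate for percentage change.

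**2. Baseline adjustment, treated subjects more variable.** Simulation with 6,000 runs per setting, regressing change on arm and baseline:

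| Treated/control residual SD ratio | 1 | 1.5 | 2 | 3 |
|---|---|---|---|---|
| Variance ratio, control-arm ρ = 0.7 | 0.85 | 0.87 | 0.92 | 0.97 |
| Variance ratio, control-arm ρ = 0.9 | 0.96 | 0.97 | 0.98 | 1.00 |
| Type I error, classical ANCOVA, ρ = 0.7 | 0.046 | 0.017 | 0.006 | 0.003 |

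Classical ANCOVA is conservative here because the larger arm is the more variable one. With HC3 robust standard errors the type I error is 0.044–0.049 at ρ = 0.7 and 0.046–0.052 at ρ = 0.9.

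**3. Stratum adjustment.** If the LFS stratum explains a share R² of outcome variance, the standard error falls by the factor √(1−R²): 0.975, 0.949, 0.894 and 0.775 for R² of 5%, 10%, 20% and 40%. Under an assumed stratum mix, the unadjusted t-test then rejects a true null in about 4.3%, 4.0%, 2.9% and 1.1% of trials against a nominal 5%. Omitting the stratum is therefore conservative, not anti-conservative.

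**4. Wilcoxon row.** Simulation with 4,000 runs per setting, 111 versus 37. Treated change is lognormal with mean 1 and log-SD 0.25, 0.5 or 0.75 (skewness 0.78, 1.75, 3.26). Control change is normal with mean 0. The interval comes from the ordered pairwise differences. Columns give control SD as a fraction of treated SD.

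| Skewness | Mean difference outside the CI: 1 / 0.5 / 0.25 | CI covers the true mean difference: 1 / 0.5 / 0.25 |
|---|---|---|
| 0.78 | 0 / 0 / 0.2% | 94.2 / 93.5 / 91.1% |
| 1.75 | 0.02 / 1.7 / 19.1% | 90.0 / 80.0 / 66.8% |
| 3.26 | 0.5 / 20.7 / 74.4% | 85.9 / 64.6 / 31.4% |

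A second parameterisation (treated median 1, control SD 0.3; 2,000 runs) shows why. With normal changes in both arms, the mean difference and the shift are both 1.00. With lognormal treated changes at log-SD 0.5, 0.75 and 1.0, the mean difference averages 1.13, 1.32 and 1.66, while the shift stays at 1.04, 1.04 and 1.05.

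**The case against.** The strongest reply is that a prespecified two-sample test on change scores is standard and valid, and that ANCOVA is a preference. The gain rests on an assumed correlation. At ρ = 0.9 with unequal variances the variance reduction is only 4% to 0%. For surface area it can vanish: a simulation with percentage change independent of baseline (assumed baseline CV 25%) gave a variance ratio of 1.01. Classical ANCOVA would also need robust standard errors to avoid being conservative. All of this stands. It limits the gain but does not make adjustment harmful.

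On the Wilcoxon row, the reply is that the SAP never says the interval belongs to the mean difference, and that medians and quartiles are reported as well. The interval also covers its own target, the median pairwise difference, in 91–98% of trials. The largest figures need both strong skew and very tight controls, and the row matters only if Wilcoxon is chosen. These points limit the consequence. They do not rescue the row: it lists one effect estimate and one interval, and a reader will pair them.

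On the labels, Protocol 8.2.2 does define surface area as a percentage in its sub-item. Only the volume label truly conflicts with the other sections, and the planned analysis can still be read from them.

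**Conclusion.** The concern holds, and the change is recommended. These are secondary endpoints, and the primary Fisher test, the sample size and the superiority conclusion are untouched.

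- **Wilcoxon row:** an error as written. It is negligible with mild skew (estimate outside its interval in at most 0.2% of simulated trials) and material with strong skew (up to 74%, with coverage of the true mean difference down to 31%). The skewness and SDs are assumed.
- **No adjustment:** a loss of efficiency, not of validity. The interval could be about 3% to 13% narrower for ρ from 0.9 to 0.5 under equal variances. The gain is smaller, possibly nil, with more variable treated responses or for percentage change. Any gain from the stratum depends on how much variance it explains, which the documents do not indicate.
- **Labels and the open choice of test:** points to tidy, which would not justify a finding on their own.

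**What to change.** 1. Name ANCOVA as the single main analysis for each endpoint: change in lip volume, and percentage change in surface area, each regressed on arm, its baseline value and baseline LFS stratum. Report the adjusted mean difference and 95% CI with heteroscedasticity-robust (for example HC3) standard errors.
2. Keep Wilcoxon as a sensitivity analysis. In that row of SAP Table 5-2, replace the mean difference with the Hodges-Lehmann shift and its own interval.
3. Correct the volume label and the surface-area heading in Protocol 8.2.2 to match the synopsis, Protocol 8.3.2 and SAP Tables 4-1 and 5-16.
4. If ANCOVA is not adopted, items 2 (the correction to the row) and 3 are still needed, and the rule for choosing between the t-test and Wilcoxon should be stated.

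**Cost.** No new data. SAP Table 5-2 already requires both baseline and month 3 values, so the same subjects are analysed. SAP Tables 5-2 and 5-16 need editing. Because the protocol synopsis and 8.3.2 name the tests, the move to ANCOVA should be made by amendment or recorded in SAP 5.3.2 before database lock. The price is a linear-model assumption and a little extra analysis.
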